Although the patient is not obliged to provide any explanation for leaving the trial prematurely, the investigator will reasonably attempt to determine the patient's motives, always respecting their rights. If a patient leaves the trial prematurely, the final visit data will be recorded in the ECRF.

The doctor may suspend the treatment at any time during the follow-up and replace it with another drug that he considers more beneficial for the patient, immediately informing the promoter of the trial.

• Treatment description and definition of exposure

Product description:

Fendrix® is a hepatitis B vaccine that contains HBsAg adjuvanted by 3-O-desacyl-4'-monophosphoryl lipid A and with aluminum phosphate. This adjuvant system is called AS04C and increases the immunogenicity of the vaccine.

- Generic name: Vaccine of Hepatitis B adsorbed and adjuvanted by AS04C
- Trade name: Fendrix®
- Laboratory: Glaxo Smithkline
- ATC therapeutic group: J07BC (Hepatitis Vaccines)
- Form of presentation: 20 µg pre-filled syringes

Fendrix® is a hepatitis B vaccine that contains HBsAg adjuvanted by 3- O-desacyl-4'-monophosphoryl lipid A and with aluminum phosphate. This adjuvant system is called AS04C and increases the immunogenicity of the vaccine. An anti-HB antibody titer \geq 10 mIU / mL correlates with protection against HBV infection. It is indicated for active immunization against infection by all known subtypes of Hepatitis B virus in patients with renal failure (including pre-hemodialysis and hemodialysis patients) older than 15 years. However, it is intended to take advantage of the greater immunogenic capacity

of this vaccine in non-responders, understood as those who have received two complete vaccination schedules without reaching an antibody titer greater than 10 mIU / mL.

Terms of administration:

Immunization will consist of a maximum of 4 doses of 0.5 ml administered according to the following schedule: 1 month, 2 months and 6 months from the date of the first dose, with an intramuscular vial in the deltoid muscle at the dose of 20 μ g, as stated in the Fendrix technical data sheet. After the administration of each of the doses, a serological analysis will be carried out (approximately 30 days after the administration of each dose), making it clear that if seroprotection is achieved (anti-HB \geq 10 mIU / ml, the administration will be suspended. of successive doses.

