The precautionary measures regarding contraindications and warnings of the product, recommended by the manufacturer and in accordance with the recommendations of the AEMPS for its use outside the technical data sheet, will be observed.

• Stages developmental

Stage 1:

- Start up:
 - Elaboration of the documentation of the final trial: latest version of the Protocol, Electronic Data Collection Notebook (ECRFe), Informed consent for the subject, etc.
 - Request to the AEMPS classification of clinical trial and recommendations for the use of the drug outside of the technical data sheet.
 - Obtaining of CEIms authorizations and necessary contracts with the centers: carried out by the Salamanca Hospital and the IBSAL (Technical Management Unit of the Salamanca Biomedical Research Institute-clinical trials area).
- Preselection of candidates (8 weeks) in the collaborating centers of:
 - Valladolid University Clinical Hospital.
 - Zamora Healthcare Complex.
 - León University Healthcare Complex.
 - Palencia University Healthcare Complex.
 - Salamanca University Healthcare Complex.

Pre-select the workers described in the target population based on the records obtained from their clinical-working histories, which have received 6 doses of conventional hepatitis B vaccine and have not exceeded 10 mIU / mL. Detection of new cases at the University Hospital of Salamanca.

Stage 2:

- Purchase of medication: coordinated from the IBSAL-Hospital de Salamanca.

- Transport of medication to the collaborating centers: from a commercial provider to the Occupational Risk Prevention Services of the participating centers.

Stage 3:

- Inclusion of participating subjects: recruitment in each center. Select the workers described in the target population based on the records obtained from their clinical-working histories, who have received 6 doses of conventional hepatitis B vaccine and have not exceeded 10 mIU / mL.
- Dosage administration, evolution monitoring and safety: Once the consent of the participant has been obtained, Fendrix® will be prescribed at a dose of 20 micrograms up to a maximum of 4 doses. The antibody titer per month of each dose of vaccine administered will be subsequently analyzed locally at each center. Possible events and adverse reactions will be detected, subsequently monitoring the applicable Pharmacovigilance.

Visits calendar from the patients:

Visits	Selection Visit	Visit1	Visittwo	Visit3	Visit4	Final visit

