Time		Month0	Month1	Month 2	Month6	Month7
Procedures and tests						
Pick up of data and tests required for the test	X					
Analytics	X		X	X	X	X
Drug administration		X	X	X	X	
Pick up of data related to other medications and adverse events		X	X	X	X	X
Completion sheet						X

Stage 4:

- Compilation of the analyzes and ECRFs from the collaborating centers to the coordinating center.
- Treatment of data and statistical analysis: coordinating center-IBSAL.

Stage 5:

- **Publication:** from the coordinating center.

- **Schedule. Plan of work**

Activity:	People involved	From (mm / yyyy)	Until (mm / yyyy)
Stage 1	8	Jan-2017	Dec-2018
Stage 2	6	May-2017	Feb-2019
Stage 3	8	Jun-2017	Jun-2019
Stage 4	7	Dec-2018	Dec-2019
Stage 5	6	Jan-2019	Apr-2020

- **Available media to carry out the test.**

The infrastructure where it will be carried out resides in the prevention services of the hospitals involved. In addition to the management support for its development by IBSAL in its Technical Management Unit (HU Salamanca). In these services there are adequate facilities, material means to carry out all the processes required for the development of the test (refrigerators, determinations of Ab, etc.)

The personnel involved in the trial are NHS personnel with extensive experience in Occupational Risk Prevention in the health field, in addition the trial will receive the necessary administrative management support from the Clinical Trials Area of the IBSAL Technical Management Unit

- **Limitations of the trial**

The main limitation of the trial will be to find new cases of non-responding workers and overcoming the difficulties of the lack of standardized records of non-responding workers from the different prevention services of the collaborating hospitals.

8. Valuation criteria and measurement instruments

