8.2. Variables to study

- Measurement of the anti-HBs antibody titer: before the first dose and one month after the administration of each dose.
- Pickup of adverse effects during administration and all those that could be

related to the vaccine and that appear within 30 days after each dose.

9. Statistical analysis

A statistical analysis of the data will be carried out, assisted by the IBSAL Biostatistics Research Group

- Sample size justification**

The sample size is based on the recruitment carried out from the previous study carried out at the Salamanca University Healthcare Complex. Considering the number of subjects susceptible to study in the different centers, a sample size of up to 80 subjects is estimated.

- Statistical methodology**

The results of the present trial and the clinical-biological data of the patients will be registered in a database.

Statistical significance: The results will be analyzed using SPSS software (version 15.0) for Windows.

An initial descriptive analysis of the quantitative variables will be carried out, which will include measures of central tendency (mean, median), measures of dispersion (range, standard deviation) and box plots, with possible extreme values. For qualitative variables, frequencies will be presented.

The level of significance will be set at $p < 0.05$.

10. Ethical aspects and legal

The researcher will carry out the study in compliance with the ethical principles of the Declaration of Helsinki.

The trial must adhere to the protocol, which guarantees compliance with Good Clinical Practices, described in the Harmonized Tripartite Guidelines of the ICH on Good Clinical Practices.

This trial will be submitted for evaluation by a Drug Research Ethics Committee and the Spanish Agency for Medicines and Health Products (AEMPS) will be notified.

The pertinent authorizations will be obtained in accordance with current regulations for clinical trials.

- Information sheet and consent form**

The researcher will explain to each patient (witness or legal representative) the nature of the trial and the purposes, procedures, estimated duration, possible risks and benefits of participating in the trial and possible inconveniences that it may cause. All patients will be informed of the voluntary nature of their participation and that they may withdraw at any time, without affecting their future medical care or their relationship with the doctor responsible for their treatment.

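### The titre objective has no log-scale summary, interval or stated analysis set, and because dosing stops on response, any titre summary by dose number could not be read as a time course

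*Combined protocol and SAP*

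**What the plan says.** Section 5 makes the analysis of anti-HBs titres, as a picture of the immune response, the first secondary objective. The analysis planned for it is the general sentence in Section 9 (Statistical methodology) on quantitative variables: "measures of central tendency (mean, median), measures of dispersion (range, standard deviation) and box plots, with possible extreme values". Qualitative variables get frequencies, and a 0.05 significance level is stated without a named test.

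The measurement times are in Section 8.2: "Measurement of the anti-HBs antibody titer: before the first dose and one month after the administration of each dose". Section 7 (Terms of administration) allows up to four doses, the later ones at "1 month, 2 months and 6 months from the date of the first dose". It adds that "a serological analysis will be carried out (approximately 30 days after the administration of each dose", and that once seroprotection at 10 mIU/mL is reached "the administration will be suspended. of successive doses". Section 7 (Stage 3) states: "The antibody titer per month of each dose of vaccine administered will be subsequently analyzed locally at each center".

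The visit calendar in Section 7 marks blood tests at selection and at months 1, 2, 6 and 7, and dosing at months 0, 1, 2 and 6. It makes no exception for subjects who have responded.

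**The concern.** There are three linked gaps.

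- **Scale and precision.** Titres are usually right-skewed. The median and box plots cope with that; the arithmetic mean and SD depend on a few high values. No interval is named. One could be built from mean, SD and n, but only on the arithmetic scale.
- **Who is summarised.** The stop rule removes a subject from later dosing because of the very variable being summarised. If titres are grouped by dose number, each group after the first is selected for low earlier titres. The median and box plot carry the same selection, so they do not cure it.
- **When titres are taken.** The calendar and the text disagree about the sample after the third dose, and neither says whether responders are sampled again.

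At stake is a named secondary objective. Titres could rise with every dose while a by-dose table shows them falling.

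**Working it through.** **1. The plan's own figure.** The only design figure is up to 80 subjects, justified by how many eligible subjects the centres have. With no power, SD or precision target there is nothing to reproduce; 80 is used below only as the starting number.

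**2. Sampling times.** Dose months from the calendar are 0, 1, 2 and 6. The next marked blood tests are at months 1, 2, 6 and 7. The gaps are 1−0 = 1, 2−1 = 1, 6−2 = 4 and 7−6 = 1 month. Sections 7 (Terms of administration) and 8.2 both call for a titre about one month after each dose, so the third gap contradicts them.

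**3. Selection by the stop rule (illustration).** The documents give no titre SD or per-dose response rates, so every input here except n and the threshold is assumed. The model for log10 titre after dose k is

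L_k = m + b(k−1) + s(√ρ·u + √(1−ρ)·e_k), with u and e_k standard normal.

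Inputs: 80 subjects; 50% at or above 10 mIU/mL after dose 1, so m = 1; s = 0.8; b = 0.3; within-subject correlation ρ = 0.7. A subject leaves dosing and testing after the first titre ≥ 10. If everyone continued, the median would be 10^(1+0.3(k−1)), that is 10, 20, 40 and 79: it doubles with each dose.

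| | Dose 1 | Dose 2 | Dose 3 | Dose 4 |
|---|---|---|---|---|
| Subjects tested | 80 | 40 | 23 | 13 |
| Median in those tested | 10 | 7.4 | 8.4 | 10 |
| Median latest titre, all dosed | 10 | 19 | 23 | 26 |

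The cumulative proportion responding follows from the numbers tested: (80−40)/80 = 50% after dose 1, (80−23)/80 = 71% after dose 2 and (80−13)/80 = 84% after dose 3.

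*Hand check at ρ = 1.* Those tested after dose 2 are the lower half after dose 1. Their median is the 25th percentile plus the rise: 1 − 0.674×0.8 + 0.3 = 0.76, and 10^0.76 = 5.8. The all-dosed latest-titre median is 14.1.

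*Range.* At ρ = 0.5 the post-dose-2 median is 9.7 against 21.4. The wider grid has 18 scenarios: 30, 50 or 70% responding after dose 1; s of 0.6, 0.8 or 1.0; b of 0.3 or 0.5. Over it, the post-dose-2 median in those tested is 18–71%, 22–74% and 32–88% of the all-dosed latest-titre median at ρ = 1, 0.7 and 0.5. It lies below the post-dose-1 median in 13, 10 and 6 of the 18 scenarios.

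**4. Does the earlier study show skew?** Section 4 gives mean, n and range for the coordinating centre's compassionate-use study. The smallest SD compatible with these sets all other values equal to (n·mean − max − min)/(n−2), with >1000 entered as 1000.

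- Baseline (n = 20 assumed): (21.00 − 9.03 − 0)/18 = 0.665; minimum SD 1.88 against mean 1.05.
- Two months (n = 19): (10929.37 − 1025.67)/17 = 582.6; minimum SD 164 against mean 575.
- One year (n = 15): (2627.70 − 1014.22)/13 = 124.1; minimum SD 230 against mean 175.

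Skew is forced at baseline and one year, but not at two months, the time point nearest to this trial's samples.

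**5. What an interval would look like.** The 95% CI for a geometric mean is 10^(mean log10 ± t·s/√n). With n = 80, t = 1.99 and assumed s of 0.5 to 0.8, it is the geometric mean multiplied or divided by 10^(1.99×0.5/8.94) = 1.29 to 10^(1.99×0.8/8.94) = 1.51.

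**The case against.** The strongest reply is that the plan contains no by-dose titre table. That is correct: Section 8.2 says when titres are measured, not how they are grouped. The calendar marks blood tests at later visits for everyone, so by-visit summaries might keep responders. It also puts the blood test and the next dose at the same visit in months 1, 2 and 6, so a responder could be dosed before the result is known. A reader might infer that the trial will report titres only in earlier non-responders. The documents do not support that. They support the narrower statement that a summary by dose number would mainly cover such subjects, and that the layout is left open.

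A reader might also infer from the earlier study that results above 1000 will distort the summaries here. That study gave a full 40 µg regimen at months 0, 1 and 6; this trial gives 20 µg doses and stops at 10 mIU/mL. In the model above, at most about 9% of last titres exceed 1000, which leaves the median and box plot untouched. The zero seen earlier was a baseline value. A rule for assay limits is still worth having, since each centre assays locally, but it is a minor part of the point.

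The skew evidence is indirect, and the plan already includes the median and presents its descriptive analysis as a first step that may be extended. All of that stands. It does not supply an interval or an analysis set, and it does not remove the selection. The simulation rests on assumptions, and post-dose-4 results are not relied on because in some scenarios as few as 0.5 of 80 subjects would be expected there.

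**Conclusion.** The point holds as an under-specified analysis of a secondary objective, plus a contradiction in the sampling calendar. The plan gives titres no log-scale summary, interval, time point or analysis set. If titres were summarised by dose number, the post-dose-2 median would understate the titre reached across all dosed subjects. It is about 39% of it in the illustration (7.4/19) and 18–88% over the whole assumed grid. Those sizes depend on log-normal titres and assumed response rates, spread and rise per dose. That groups after doses 2 to 4 are selected for earlier non-response follows from the stop rule, provided it is applied as written.

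A reader might go further and doubt the efficacy result. The documents give no ground for that here: the proportion at or above 10 mIU/mL does not change with the choice of titre summary. This should be corrected before analysis, but it does not threaten the main response outcome.

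**What to change.** Add a paragraph to Section 9:

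- Keep the median and box plots. For post-dose titres, replace mean and SD by the geometric mean titre with 95% CI, computed on the log10 scale.
- State how results below or above each local assay's limits enter the analysis, and report how many are affected.
- Make the main titre summary each dosed subject's last post-dose titre, in all dosed subjects and not responders only. Describe it as the titre reached under the stop-at-10 rule, and give with it the cumulative proportion at or above 10 mIU/mL by dose number.
- Label any per-dose titre table as conditional on no earlier response, and show the number tested.
- Reconcile Section 7 (Terms of administration), the visit calendar and Section 8.2 on who is sampled and when, before the tables are fixed.

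The analysis changes need a few lines of code and no new data. The costs are some loss of comparability with the earlier study's arithmetic means, a geometric mean that depends on the rule chosen at the low limit, and possibly altered sampling once the calendar is reconciled.

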For its part, Directive 2010/32 / EU of May 10, 2010, which applies the Framework Agreement for the prevention of injuries caused by sharp instruments in the hospital and health sector and article 6 of Order ESS / 1451/2013, of July 29, which transposes the previous Directive, establishes that "vaccination must be offered free of charge to all workers and students who carry out health and related activities in the workplace": In the case of not acceptance of the offered vaccination must be recorded in writing of this decision.

The inclusion of this population of university students will be subject to the specific instructions on occupational prevention in each autonomous community. In the case of centers located in the Community of Castilla y León, their inclusion will be made based on the document "Instructions of the Ministry of Health of the Junta de Castilla y León of October 11, 2013" (link: http://www.sanidad.ccoo.es/comunes/recursos/15617/doc287408_Instruccion_de_la_gerenciaRegional_de_Salud_sobre_adopcion_de_medidas_de_prevencion_de_riesgos_y_salud_laboral_para_los_estudiantes_que_realizan_sus_practicas_df_que_realizan_sus_practicas_df

Therefore, it is proposed to carry out a broader study involving as collaborators several hospitals belonging to the NHS and the expansion of the target population.

5. goals

- **Main goal**

1. Benefit and equip NHS staff with an additional protection tool against hepatitis B infection.
2. To evaluate the efficacy of the adjuvanted vaccine in healthy subjects NON-responders to the conventional hepatitis B vaccine.

- **Secondary objectives**

1. Analyze results of anti-HBs antibody titers to see the immune response to the adjuvanted vaccine.
2. Evaluate safety results and clinical tolerance of the adjuvanted vaccine.

6. Source and information field

The source and field of information will be the electronic data collection notebook (ECRFe) that the researcher will fill in based on the patient's medical history.

7. Trial Design

- **Design:** open, multicenter clinical trial with use of off-label medication.
- **Duration:** 2 years
- **Ambit study:** Services of Prevention of Occupational Risks of the public hospitals of the NHS

The multicenter trial will be carried out in the following hospital centers:

- University Clinical Hospital from Valladolid. ([name] [name])
- Healthcare Complex of Zamora. ([name] [name])
- University Healthcare Complex of Lion. ([name] [name])

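### The post-dose-3 titre falls 1 month after the dose in the text but 4 months after in the visit calendar, and section 9 does not say how the efficacy proportion is formed when dosing stops on response

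*Combined protocol and SAP*

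**What the plan says.** Section 5 lists as a main goal "To evaluate the efficacy of the adjuvanted vaccine in healthy subjects NON-responders to the conventional hepatitis B vaccine". It attaches no endpoint, time point or denominator.

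Section 7, Terms of administration, allows up to four doses, the later ones at "1 month, 2 months and 6 months from the date of the first dose". Serology is to follow "approximately 30 days after the administration of each dose", "making it clear that if seroprotection is achieved" (anti-HBs of at least 10 mIU/mL) later doses are suspended. Section 7, Stage 3, agrees: "The antibody titer per month of each dose of vaccine administered will be subsequently analyzed locally at each center". Section 8.2 lists the titre before the first dose and one month after each dose.

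The visit calendar in section 7 has a selection visit and then Months 0, 1, 2, 6 and 7. Its rows read "Drug administration X X X X" (Months 0, 1, 2 and 6) and "Analytics X X X X X" (selection, then Months 1, 2, 6 and 7).

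Section 9 plans means, medians, ranges, standard deviations and box plots for quantitative variables. For the rest, "For qualitative variables, frequencies will be presented". It sets a 0.05 significance level but states no hypothesis.

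**The concern.** Two things are at stake.

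**Measurement.** If the post-dose-3 titre is taken at Month 6, it is not comparable with the titres taken one month after the other doses. The draw also falls at the visit where the next dose is given. The two readings can therefore give different dose-3 response rates and a different group receiving dose 4. The calendar does not say whether people who have stopped dosing still attend for later draws.

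**Estimation.** Under stop-on-response dosing, the same data support a cumulative rate over everyone dosed and a rate among those still being dosed. These can differ widely, and section 9 commits to neither. Mean titres and box plots after doses 2 to 4 are open to the same selection. With the choice left open, it could be made after the results are seen.

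**Working it through.** **1. Dose-to-draw gaps.** Dose months (0, 1, 2, 6) are the same in Terms of administration and the calendar. Draw months (1, 2, 6, 7) come from the calendar.

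| Dose | Given | Due at one month | Next calendar draw | Gap |
|---|---|---|---|---|
| 1 | Month 0 | Month 1 | Month 1 | 1 month |
| 2 | Month 1 | Month 2 | Month 2 | 1 month |
| 3 | Month 2 | Month 3 | Month 6 | 4 months |
| 4 | Month 6 | Month 7 | Month 7 | 1 month |

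The conflict does not depend on how the marks line up in the extracted table, because the calendar has no column between Months 2 and 6.

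The pilot in section 4 shows that response status can change with time. Nineteen of 20 responded at two months (19/20 = 95%). Two responders were not followed to one year, leaving 19 − 2 = 17 responders followed. Only 15 people were at or above 10 at one year, so at least 17 − 15 = 2 responders had fallen below it. That was another regimen and a longer interval, so it shows the possibility and not the size.

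**2. By-dose rate against cumulative rate.** Let p_k be the response rate at dose k among those not yet responding. With complete titres and prompt results, cumulative = 1 − Π(1 − p_j) ≥ 1 − (1 − p_k) = p_k. A rate after any one dose then cannot exceed the cumulative rate.

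The documents give no per-dose rates, so these are assumed. Take N = 80 (the maximum in section 9), no missing titres and an equal rate p = 1 − (1 − C)^(1/4). The cumulative rate C is set at 75% (assumed low case), 95% (the pilot's rate) or 98% (the rate cited in section 4).

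| C | p = rate after dose 4 | Numbers given doses 1, 2, 3, 4 |
|---|---|---|
| 75% | 29.3% | 80, 56.6, 40.0, 28.3 |
| 95% | 52.7% | 80, 37.8, 17.9, 8.5 |
| 98% | 62.4% | 80, 30.1, 11.3, 4.3 |

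**3. Results one visit late.** Suppose responders get one further dose before the result is known and stay at or above 10. The dose-4 group is then 80(1 − p)² = 40.0, 17.9 or 11.3 people. The rate after dose 4 is 1 − (1 − p)² = 50.0%, 77.6% or 85.9%. The gap narrows but remains.

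**4. Falling rates.** With 50, 40, 30 and 20% at successive doses, cumulative = 1 − 0.5 × 0.6 × 0.7 × 0.8 = 83.2%. The rate after dose 4 is 20% (n = 16.8) with prompt results. One visit late it is 1 − 0.7 × 0.8 = 44% (n = 24).

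**5. Limit of the bound.** Suppose 40 of 80 respond to dose 1, 30 are lost, and 9 of the remaining 10 respond to dose 2. The post-dose-2 rate is 90%. The cumulative rate with missing counted as failure is 49/80 = 61%. The inequality in step 2 therefore needs complete titres.

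**6. Precision of a cumulative estimate (Clopper-Pearson 95%).** 76/80 = 95.0% (87.7 to 98.6). The pilot's 19/20 gives 75.1 to 99.9.

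**The case against.** The strongest reply is that section 9 promises no by-dose response rates and presents none as efficacy. By-dose reporting is inferred from the per-dose titre variable in section 8.2. Frequencies would permit a cumulative proportion, and the pilot counted responders over all 20 participants. This stands: a reader might infer that the plan will report conditional rates as efficacy, and the documents do not support that. What remains is that the proportion is left undefined. The pilot points towards a cumulative rate but does not bind this plan.

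Three other strong readings also fail.

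- *A later by-dose rate must understate efficacy.* Only with complete titres; step 5 shows the reverse under heavy dropout.
- *The calendar makes the stopping rule unworkable before dose 4.* No result turnaround is stated. The text alone also puts the titres after doses 1 and 2 at about the time doses 2 and 3 are due, so the question is neither peculiar to dose 4 nor created by the conflict.
- *Every summary after dose 2 covers earlier non-responders only.* Not if results come late or draws continue for everyone.

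It can also be said that one calendar and delegated monitoring make divergence between centres hypothetical. That is fair, but the contradiction exists even if every centre follows the same passage.

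Concerns about baseline titres and missing data are minor. The calendar has a blood test at selection, section 11 requires eligibility to be verified, and section 7 records final-visit data for early leavers. None of these defines the analysis denominator.

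**Conclusion.** The point holds in two parts.

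First, sections 7 and 8.2 contradict the visit calendar on the post-dose-3 titre: 1 month after the dose against 4 months. This follows from the stated schedule without any assumption. It affects comparability across doses and can affect who is given dose 4.

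Second, section 9 does not form an efficacy proportion for a main goal under stop-on-response dosing. The consequence is a risk of selective or misread summaries. Its size rests on assumed rates: in the equal-rate illustrations, the rate after dose 4 is 29 to 62% against a cumulative 75 to 98% with prompt results, or 50 to 86% with results one visit late. The direction is assured only with complete titres and prompt results.

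The plan should be changed on both counts. The documents do not show that a biased estimate is planned.

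**What to change.** (a) Reconcile Terms of administration, Stage 3 and section 8.2 with the visit calendar. State when the post-dose-3 titre is taken and who is tested after dosing stops. Which passage is right is for the sponsor and investigators; this review does not say.

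(b) In section 9, make the main efficacy estimate the cumulative proportion with any post-dose anti-HBs of at least 10 mIU/mL. The denominator is everyone who received at least one dose and was below 10 at the baseline draw. Give an exact (Clopper-Pearson) 95% interval. Count people with no recorded titre of at least 10 as non-responders, and add a measured-only sensitivity result.

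(c) Show response by dose cumulatively over that same denominator. For any per-dose rate, mean, median or box plot after doses 2 to 4, state its n and who is in it: earlier non-responders only, or also responders dosed or tested before their results were known.

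Cost: (b) and (c) add no participants, visits or draws. Part (a) may add or remove a draw, depending on how the passages are reconciled. Section 10 exempts only administrative changes from committee approval, so an amendment is probably needed. The main rate will be somewhat less favourable than a measured-only rate: with an assumed 64 responders and 4 people unmeasured, 64/80 = 80.0% against 64/76 = 84.2%.
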